#### **3.5.4 Consent Procedures**

Phase 1 and 2: The study will be explained to the potential participant by the Principal Investigator or trained study staff via phone. The PI or study staff will review essential elements of consent and answer any questions. Interested and eligible participants will be emailed a link to an online consent form prior to starting the program. To consent, potential participants will be instructed to click "submit the form" button in order to consent.

Phase 3A: The study will be explained to the potential participant by the Principal Investigator or trained study staff in person or on the phone. All subjects will receive a

copy (paper or electronic) of the consent form. To document the process of the consent, we will complete “documentation of Consent Process” form to document that 1) study subjects were provided with a copy of the Consent Forms, 2) all essential elements of informed consent were discussed with subjects, 3) subjects were given adequate time to read and discuss the study with study staff, and 4) all questions asked by the subjects about the study were answered.

Phase 3B: As done in Phase 2, the study will be explained to the potential participant by the Principal Investigator or trained study staff via phone. The PI or study staff will review essential elements of consent and answer any questions. Interested and eligible participants will be emailed a link to an online consent form prior to starting the program. To consent, potential participants will be instructed to click “submit the form” button in order to consent. Since consent forms will be completed online, we are requesting a waiver of documentation of consent.

### ***3.5.5 Subject Costs and Compensation***

Phase 1: Participants who drive to the Rutgers Cancer Institute of New Jersey to complete an interview will incur parking costs. Participants will be given \$25 for completion of an interview.

Phase 2: Peer mentors will be asked to travel to the Rutgers Cancer Institute of New Jersey for training; they will be compensated \$100 for their time and travel. Peer mentors and participants will be asked to use their personal phone for communication via phone and text, which may incur costs depending on the participants’ phone plan. Peer mentors will be compensated \$100 per participant mentored to cover costs and effort. Participants will receive \$25 per assessment completed (for a total of \$50).

Phase 3A: There are no anticipated costs of completing usability testing. Participants will receive \$25 gift card for each usability session completed, up to 5 sessions.

Phase 3B: Similar to Phase 2, peer mentors will be asked to travel to the Rutgers Cancer Institute of New Jersey for in-person training or attend via videoconference/webinar. They will be compensated \$75 for their time/travel. Peer mentors and participants will be asked to use their personal phone for communication via phone and text, which may incur costs depending on the participants’ phone plan. Peer mentors will be compensated \$75 per participant mentored to cover costs and effort. Participants will receive \$50 per assessment completed (for a total of \$200).

## **4. Study Variables**

### ***4.1 Independent Variables or Interventions***

Phase 1: Semi-structured interview guides will be used to conduct interviews. The goal of the interviews is to understand patient, parent, and provider perspectives on the challenges faced by AYAs in managing their health care and on how PSST materials can be adapted to address the challenges of self-management of care.

Phase 2: Independent variables include demographics (age, gender, socioeconomic status, education, employment status, living at home or independently) and cancer diagnosis and treatment history (i.e., diagnosis, time since treatment completion, types of treatment received). Diagnosis and date of diagnosis will be obtained from NJSCR records and the remaining information from self-report.

## Promoting Follow-Up Care Self-Management for Adolescent and Young Adult (AYA) Childhood Cancer Survivors

[name], MPH

Phase 3A: Demographics (age, gender, socioeconomic status, education, employment status, living at home or independently) and cancer diagnosis and treatment history (i.e., diagnosis, time since treatment completion, types of treatment received) will be collected by self-report.

Phase 3B: Same as Phase 2.

**Phase 2: Peer Mentoring Intervention.** Based on initial interviews and feedback on the PSST intervention, we identified five major themes to be addressed in our program. The intervention will include two components: (1) online self-management educational modules using the Rutgers Canvas online course platform and (2) weekly video-conference calls on Doxy.me between the peer mentor and participant. Table 1 shows the content of the five online modules based on preliminary work. Participants are expected to complete one module per week in addition to a call with their mentors. Each module takes approximately 30 minutes to complete and ends with a personalized assignment for the participant to complete on his/her own (e.g., obtain survivorship care plan, make an appointment, practice communication skills).

Participants will be matched with a peer mentor of the same sex and cancer type to the extent possible. The objectives of the first mentor call are to build rapport, exchange stories regarding current long-term follow-up care, and identify the participant's self-management strengths, weaknesses, and goals. During this call, the mentor will explain that the mentee is expected to complete one online module per week prior to their next scheduled mentor call (one a week for six weeks). The dose was chosen based on other peer mentoring programs that employed weekly Skype calls. Weekly video-conference calls will be made on HIPAA compliant Doxy.me (<https://doxy.me/>) that implements security and encryption protocols to assure that data integrity and privacy is maintained. In addition to weekly calls, the mentor will encourage the participant to work through the assignment and modules via a weekly text message (using TigerText, a HIPAA-compliant program) to offer encouragement, support, and relevant resources. Mentor-mentee calls will be recorded and text messages will be archived for supervision and content analysis.

Given that AYAs are high consumers of technology and tend to have many different educational, work, and social scheduling demands, we believe using online educational modules and technology to connect the peer mentor and participants will be the most efficient delivery system for this group. To capitalize on AYAs' regular use of technology, peers will provide support and facilitate completion of educational modules via 6 weekly phone calls and secure text messaging. We will utilize the TigerText service that will allow for secure messaging between participants and peer mentors, as well as between the study personnel, peer mentors, and participants.

**Table 2. Content of self-management modules**

Module	Proposed Content	Transition Readiness Construct
1	Understanding Treatment History and Survivorship Care Plan 

• Name diagnosis, treatments received, risks for late health effects

• Obtain (if needed) and store Survivorship Care Plan

• Identify necessary health screenings and frequency

	Knowledge Goals/motivation
2	Managing Your Health Care 

• Review self-management tasks (e.g., make appointments, obtain screenings)

• Establish and maintain relationship with primary care doctor

• Logistics of insurance and healthcare tasks

• Identify barriers to obtaining care and problem solve

	Self-Management Skills Self-efficacy Relationships/communication Goals/motivation

## Promoting Follow-Up Care Self-Management for Adolescent and Young Adult (AYA) Childhood Cancer Survivors

[name], MPH

	

• Review motivation and confidence to assume responsibility for care

	
3	Negotiating Family Involvement in Your Care 

• Discuss challenges of parents who do not relinquish control & communication skills

• Discuss supportive ways to include family

	Relationships/communication
4	Dealing with Emotions about Your Health and Follow-Up Care 

• Coping with uncertainty of future health

• Communicating with providers & families about adult-oriented healthcare

	Self-Management Skills Relationships/communication
5	Staying Healthy in the Context of Life Transitions 

• Recognize that health must be maintained in the context of other important life transitions (e.g., education, career, relationships)

• Skills & resources for healthy diet, exercise, sexual health/fertility, education, career

• Identify value in prioritizing health

	Goals/motivation Self-Management Skills Self-efficacy

**Peer Mentor Training.** Peer mentors will attend a one-day training workshop conducted by the PI and study staff (similar to other peer mentor programs). Peer mentors will be given the Peer Mentor Handbook, a manual adapted from the National Mentoring Research Center, which details their roles, responsibilities, and an outline for each mentor call. Presentations, interactive discussions, and role plays will be used to teach mentors how to facilitate their mentee's use of the online self-management modules, and how to provide informational and emotional support to their mentees. Ethical issues, including confidentiality and setting boundaries with peers, will be discussed. Peer mentors will also be instructed in how to securely transfer audio recordings of their calls with mentees and destroy the original file from their devices. In addition to the in-person training, we will email these instructions. Peer mentors will have regular weekly phone supervision with the PI or trained study staff once assigned mentees to review mentoring calls and discuss any challenges experienced. During this supervision call, the PI or research staff will verbally confirm that peer mentors have destroyed any transferred audio recordings for the study.

**Phase 3B: Self-Management + Peer Mentoring Intervention.** The intervention content is the same as described in Phase 2. There are a few minor differences: (1) the online modules will be hosted on its own website instead of Canvas; this website will be built in Phase 3A using Radian Creative Group, LLC, an experienced technology development firm that has a strong history of collaboration with [name] and other Rutgers Cancer Institute of New Jersey investigators; (2) TigerText is now called TigerConnect and has expanded its services to include secure videoconferencing; therefore, doxy.me will no longer be used; and (3) peer mentor training can be completed either in-person or via videoconference to minimize peer mentor burden.

**Phase 3B: Usual Care Comparison.** The Usual Care group will complete surveys only. To select an appropriate comparison, we reviewed the literature of advantages/disadvantages of different designs. This study can be characterized as a phase IIb feasibility pilot focused on feasibility and acceptability, as well as detecting a clinically significant signal over noise. A usual care comparison group is recommended for initial evaluations of such interventions, as it maximizes statistical power and protects against falsely concluding that the intervention lacks efficacy. We will offer access to the online educational modules upon completion of all study procedures to the interested subjects in the usual care comparison group.

### 4.1.1 Drug or Device Interventions

N/A

Protocol Version 3 12.13.2020

CINJ# 131507

#### **4.2 Dependent Variables or Outcome Measures**

Phase 1: The primary outcome measure is qualitative interview data. Interviews will be transcribed for analysis (see Data Handling and Statistical Analysis section for details). Participants will also be asked to complete the questionnaires selected for Phase 2 and provide feedback to the study staff regarding how well the questionnaires capture self-management of survivorship care.

Phase 2: The following standardize measures will be administered at baseline and immediately post-intervention (~6 weeks), except where noted:

*Transition readiness.* The Readiness for Transition Questionnaire – Survivor Version (RTQ) is a 22-item scale evaluating transition readiness for cancer survivors. Respondents are asked to rate the degree to which they are responsible for various aspects of their health care, such as knowing their survivorship care plan, scheduling visits, and filling prescriptions. They are separately asked to rate the degree to which their parents are responsible for managing the same aspects of their care. Two questions ask about the survivors' overall perception of their readiness to transfer to an adult-approach to health care. The RTQ has demonstrated adequate reliability.

The Transition Readiness Inventory (TRI), developed using the SMART framework, is a comprehensive measure of multiple components of transition readiness. While the RTQ focuses on responsibility for behaviors, the TRI focuses on behaviors *and knowledge, attitudes, and beliefs*. Specifically, the TRI yields a total score and provides scales for the following targets of our intervention: knowledge, self-management skills, self-efficacy for managing care, goals/motivation, and communication with family and providers around survivorship care. The TRI has shown adequate reliability and content validity, and evidence of predictive validity of engagement in adult healthcare. We will utilize the total TRI score.

*Negative Affect.* PROMIS Depression and PROMIS Anxiety measures are validated 8-item measures of depressive symptoms and anxiety. We will examine cancer-related anxiety using the Fear of Recurrence Scale, which has been used with young adult survivors of childhood cancers. Finally, we will adapt items to examine anxiety related to healthcare transition and cancer late effects. We will also use the Cancer Related Worry Scale to assess participants' concerns related to their cancer past and future.

*Impact of Cancer.* Three subscales from the Impact of Cancer – Childhood Cancer Survivors Scale will evaluate perceptions of impact on body and health, memory and thinking, and personal growth. Participants will be asked to complete all three subscales; mentors will be asked to complete body and health and personal growth only to evaluate if mentoring has positive effects on these outcomes.

*Perseverance.* The Short GRIT Scale is an 8-item measure of perseverance for long-term goals. We will examine the total score as a correlate of transition readiness and adherence to follow-up care.

*Barriers to follow-up care & adherence.* We will evaluate insurance status, current provider, and other barriers to care with the Follow-Up Care Use and Health Outcomes of Cancer Survivors (FOCUS) measure. Participants will report on appointments, cancer screenings, and other adherence markers.

**Promoting Follow-Up Care Self-Management for Adolescent and Young Adult (AYA) Childhood Cancer Survivors**

[name], MPH

*Treatment Integrity.* Peer mentors will record their video/phone conversations with participants for supervision with the PI. Additionally, 10% of tapes will be randomly selected for treatment integrity review using a checklist of the core components of each session.

*Mentor/Participant Alliance.* A brief measure of personality (Ten Item Personality Inventory) will be administered to participants and mentors at baseline only to examine whether personality matching relates to perceived relationship alliance. A brief measure of the alliance between the mentor and participant (Working Alliance Inventory – Short Form^41) will be completed by mentors and participants at post-intervention only.

*Satisfaction with Intervention.* At the 6 week post-intervention assessment, participants will be asked to complete a survey regarding their satisfaction with the intervention received and recommendations for improvement. For the intervention group receiving the online modules and peer mentor, items from a standardized set of internet-based intervention evaluation tools will be used - Internet Intervention Utility Questionnaire, Impact Questionnaire, and Adherence Questionnaire. The Utility Questionnaire measures perceived usefulness, enjoyment, and ease of use. The Impact Questionnaire measures perceived effectiveness in improving targeted skills. The Adherence Questionnaire measures barriers to engagement. Objective user data (i.e., log-ins, posts, modules completed) will be obtained unobtrusively from Canvas. Peer mentors will be given an interview (i.e., Peer Mentor Interview) at the end of the program to assess their thoughts about the program (what went well, did not work well, etc.) The participants will also be asked to do a brief (~20 minute) phone exit interview with the PI or the study staff to gather qualitative feedback on how to improve the program in the future (see Participant Exit Interview Guide).

**Phase 3A:** The primary outcome measure is qualitative interview data and participant report on a brief standardized internet-based intervention evaluation tool, the Visual Aesthetics of Websites Inventory. Notes will be taken during usability sessions.

Phase 3B: Feasibility outcomes include treatment fidelity, satisfaction, acceptability, usability/engagement with the online modules, and acceptance/engagement with the peer mentor. These will be measured via survey and objective user analytics for the online modules. Behavioral outcomes include transition readiness, fear of recurrence, barriers to follow-up care, adherence to follow-up care, adherence to general healthcare practice recommendations, self-efficacy (i.e., general, survivorship care specific, health insurance, communication, managing emotions), perceived emotional and informational support, perceived stigma/shame associated with cancer survivorship, healthcare utilization behaviors, and health behaviors (i.e., tobacco, alcohol, exercise, sedentary). The survey consists of validated measures of each construct or items drawn from validated instruments including the BRFSS 2018, NHANES 2013-2014, HINTS, and CCSS. The table below indicates the items and time points for administration.

At the last follow-up, we will also ask participants to sign medical record release forms to share medical information from their cancer-related physician(s) and primary care physician(s) to verify healthcare utilization during the study period. These forms will be available to participants either via regular mail, along with a postage-paid return envelope, and/or a link to the electronic copy of the form, requesting an electronic signature, hosted by the HIPAA compliant Qualtrics data collection tool.

**Promoting Follow-Up Care Self-Management for Adolescent and Young Adult (AYA) Childhood Cancer Survivors**

[name], MPH

Once the Medical Record Release form is completed, signed and returned along with the contact information of the doctors visited in the last 12 months, we will verify the contact information provided by the patient for completeness against publicly available data on the web. We will then mail, email, and/or fax the request for information to the doctor (depending on the contact information available) along with a cover letter and a copy of the signed medical record release form for the patient. We will follow-up with up to three phone calls or emails to the doctor/doctor's office if we do not receive a response to our request. We will request the following information: survivorship care plan/treatment summary (if available), dates and types of visits in the past 12 month (i.e., preventive care, survivorship care, or sick visit) and dates and types of medical screening tests/labs completed in the past 12 months.

Measure	Time Point			
	Baseline	Post-Intervention (~8 weeks)	Follow-Up (~5 months)	Follow-Up2 (~12 months)
Readiness for Transition Questionnaire – Survivor Version (RTQ)	x	x	x	x
Transition Readiness Inventory (TRI)	x	x	x	
Fear of Recurrence Scale 	x	x	x	
Perceived public stigma and internalized shame 	x	x	x	
Self-efficacy (general, cancer-survivorship, health insurance, communication)	x	x	x	x
Follow-Up Care Use and Health Outcomes of Cancer Survivors (FOCUS)	x		x	x
Healthcare Practices (i.e., general physical exam, immunizations, dentist, cancer screenings)	x		x	x
Health behaviors (i.e., tobacco, alcohol, exercise, sedentary)	x	x	x	
PROMIS -Self-Efficacy for Managing Chronic Conditions-Managing Emotions -Information Support -Emotional Support	x	x	x	x (Information & Emotional Support only)
Chronic Disease Self-Efficacy: Communicate with physician scale 	x	x	x	x
Working Alliance Inventory – Short Form 		x		
Internet Intervention Utility Questionnaire, Impact Questionnaire, and Adherence Questionnaire.  &		x		

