#### ***3.1. Duration of Study***

Phase 1: Participants will be asked to complete a one-time interview lasting approximately 60 minutes.

Phase 2: Participants will be asked to complete the intervention over a period of 6 weeks. Participants will be asked to complete 6-week online self-management educational modules and 6 weekly peer mentor calls to facilitate engagement with the online modules and offer specialized support.

Phase 3A: Usability sessions will last approximately 1-hour. Given that usability testing is iterative and design changes are made in response to participant feedback, we will ask some participants if they are willing to review the product another time after changes are made, up to a total of five times. Each session is voluntary and conducted in a way to minimize participant burden.

Phase 3B: Participants assigned to the intervention will be asked to complete it over a period of approximately 8 weeks (which includes 6 peer mentor calls and five corresponding online modules). All participants will be asked to complete surveys at four time points: baseline, immediate post-intervention (~8 weeks after baseline), 3-month follow-up (~5 months after baseline), and 9-month follow-up (~12 months after baseline).

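### The 12-month look-back in the Phase 3B record request has no anchor date, so late requests can miss the first months of the study period it is meant to verify

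*Combined protocol and SAP*

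**What the plan says.** All references are to the combined protocol and SAP.

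- **Purpose (section 4.2, Phase 3B).** Records are sought "to verify healthcare utilization during the study period".
- **Timing of the form (section 4.2, Phase 3B).** "At the last follow-up, we will also ask participants to sign medical record release forms". Section 3.1 places that visit at "9-month follow-up (~12 months after baseline").
- **Steps before the request (section 4.2, Phase 3B).** The next step begins "Once the Medical Record Release form is completed, signed and returned along with the contact information of the doctors visited in the last 12 months". Staff then check the contact details against public sources and send the request. No time limit is set for any of this.
- **What is requested.** Offices are asked for "dates and types of visits in the past 12 month" and for "dates and types of medical screening tests/labs completed in the past 12 months". The care plan or treatment summary is also requested, with no look-back attached.
- **Reminders.** "We will follow-up with up to three phone calls or emails to the doctor/doctor's office", again with no time limit.
- **Doctor list.** Section 5 (Phase 3B, Data Management) also uses an undated 12-month look-back when asking participants which physicians they have seen, and treats it as the study period.
- **Use of the data.** Section 1.1, Hypothesis 5, expects more survivorship and preventive care in the intervention arm than under usual care. Section 5 classes adherence to appointments and screening as exploratory. The measures table in section 4.2 also collects self-reported care (FOCUS and Healthcare Practices) at baseline, about 5 months and about 12 months.

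No passage gives the date from which the 12 months are counted, or a rule for cutting the records to the study period.

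**The concern.** The purpose is stated in study time, but the request is stated in relative time. The two coincide only if the look-back is counted from a point exactly 12 months after randomisation. Because the form is first offered at about that point, every step that follows can only push the request later. A doctor's office that receives an undated 12-month request would most naturally count back from the letter, and a participant listing doctors would count back from the day of filling in the form.

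The months at risk are the first ones, which contain the roughly 8-week intervention. The module assignments in section 4.1 include booking an appointment, so some care prompted by the programme could fall there. The 5-month survey also asks about care, and checking those answers needs records from the early months. The doctor list adds a second route to loss: a doctor seen only early in the study may not be listed if the form is completed late, and would then never be contacted.

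**Working it through.** The plan states no figure for this point, so there is nothing to reproduce. The check is calendar arithmetic.

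**Inputs**
- Final assessment F = 12 months after baseline (section 3.1 and the measures table in section 4.2).
- Look-back = 12 months (section 4.2).
- Intervention = 8 weeks (section 3.1) = 56 days / 30.4375 days per month = 1.84 months.
- Delay d from the final assessment to the point from which the look-back is counted: **not given**. It is assumed here to lie between 0 and 6 months.
- Baseline and randomisation are treated as the same date.

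**Formulas** (months after baseline)
- Window covered = [F + d − 12, F + d].
- Study months missed at the start = max(0, F + d − 12).
- Time after the final assessment inside the window = d.

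**Results with F = 12**

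| Delay d | Window | Missed at start | Share of year | Share of 8-week intervention missed |
|---|---|---|---|---|
| 0 | 0 to 12 | 0 | 0% | 0% |
| 0.5 | 0.5 to 12.5 | 0.5 | 4% | 0.5/1.84 = 27% |
| 1 | 1 to 13 | 1 | 1/12 = 8% | 1/1.84 = 54% |
| 1.84 | 1.84 to 13.84 | 1.84 | 15% | 100% |
| 3 | 3 to 15 | 3 | 25% | 100% |
| 6 | 6 to 18 | 6 | 50% | 100% |

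**Sensitivity to the date of the final assessment.** Section 3.1 calls the last visit a 9-month follow-up. Counted from the 8-week assessment, as the 3-month follow-up at about 5 months appears to be, it would fall at 1.84 + 9 = 10.84 months. Then:
- d = 0: the window starts at 10.84 − 12 = −1.16, so it covers 1.16 months before baseline and misses nothing.
- Nothing is missed until d exceeds 1.16 months.
- d = 2: 0.84 months missed (0.84/10.84 = 8% of follow-up; 0.84/1.84 = 46% of the intervention).
- d = 3: 1.84 months missed (1.84/10.84 = 17% of follow-up; all of the intervention).

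**What can be repaired afterwards.** The request asks for dates, so visits before baseline or after the final assessment can be removed. Visits in months that were never requested, or to doctors who were never listed, are absent from the returned records and cannot be restored from them.

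**With fixed dates.** If the request names the randomisation date and the final assessment date, the months missed and the months outside the study are both 0 at any d and for either F.

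**The case against.** The best defence is that the look-back is shorthand. The form is offered at about month 12, the purpose is the study period, and section 5 equates the two. The release form and cover letter, which may carry exact dates, are not among the documents. On that reading nothing is lost. The defence shows what was intended, but the protocol text still gives no anchor and no time limit for the steps before the request.

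A reader might infer four stronger conclusions that the documents do not support:

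- **That the look-back is defined as running from the request.** It is undefined. Counting from the request is only the natural reading.
- **That post-study or pre-randomisation visits will enter the outcome.** Dates are requested, so such visits can be trimmed. What is missing is a written rule to do so.
- **That a quarter of the year, or the whole intervention period, will be lost.** Both depend on a delay the plan does not give, and both shrink if the final assessment falls at 10.84 months. Reminders follow the request, so they do not move a window counted from it. They would matter only if an office counted back from its own reply.
- **That Hypothesis 5 will be biased.** The same procedure applies to both arms, and nothing shows that delay differs by arm. The care plan is requested without a look-back, so that item is not exposed. An appointment booked during the programme may also take place after it.

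It also stands that the records check self-report and are not described as the sole source of utilization data.

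**Conclusion.** The point holds as a minor defect of definition. The stated purpose is the study period, while the record request and the doctor list use an unanchored 12 months that begins to drift once the final assessment has passed. If people count back from when they are asked and the final assessment is at month 12, the loss is one month at the start for each month of delay: nothing if on time, about 8% of the year at an assumed 1 month, and the full 8-week intervention at about 1.8 months. If the assessment is at 10.84 months, loss begins only after a delay of 1.16 months.

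The consequence is an observation window that varies between participants and may blur an early difference in care use. It affects an exploratory measure, used for verification, that bears on Hypothesis 5. The RTQ analysis and the feasibility decision rules do not depend on it.

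**What to change.** In the release form, the doctor-contact question and the cover letter, replace the relative look-back with two calendar dates for each participant: the randomisation date and the date of the final (about 12-month) assessment. Ask for visits, screening tests and labs between those dates, and for all doctors seen between them. State in section 5 that only events within that window are counted.

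Ending the window at the actual final assessment means it has already closed when the request goes out, whether that visit falls at about 10.8 or 12 months. Any small variation in window length is then known from the dates.

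The cost is wording in three documents, one sentence in the analysis section and two dates filled in per participant. No extra data collection or additional contact with offices is needed.
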